A protocol deviation refers to any change, non-compliance, or departure from the approved protocol such as enrolling a participant who did not meet all the inclusion/exclusion criteria, visit non-compliance, incorrect execution of the consent form, participant declines to complete scheduled research activities, use of unapproved recruitment procedures, use of an unapproved version of the Participant Information and Consent Form, dispensing or dosing error for study medication/drug, and any change, divergence, or departure from the study design or procedures defined in the protocol. The per-protocol (PP) population is a subset of the Intention-To-Treat (ITT) population, which includes participants who completed the study without any major violations of the protocol. Description of which protocol deviations will be summarized. No participants will be excluded from the ITT analyses due to protocol deviations.

Statistical Software

The analysis will be carried out using Stata (StataCorp LP, USA) and R statistical software.

Missing Data

The missing WSRS scores at week 24 for participants with available week 12 data will be imputed based on their WSRS scores at week 12. For participants with missing WSRS scores at week 12, no imputation will be performed. In the ITT population, imputation for this outcome will be conducted as described above.

Outlier data

Outliers are identified by examining standard charts, and those that are visually "distinct" are evaluated to check the impact on the results by comparing the results of the analysis with and without outliers.

Data Transformations

No transformations of raw data are planned prior to statistical analysis. All variables will be analyzed using their original measurement scales, unless transformation is deemed necessary during model diagnostics. In such cases, justification and details will be documented in the statistical outputs and Clinical Study Report (CSR).

Multiple comparisons and multiplicity

No formal procedures for multiplicity adjustment are planned for this study, as the study was not designed to perform multiple statistical comparisons for primary or key secondary endpoints. Therefore, the overall Type I error rate will not be adjusted.

Covariate Adjustment

No covariate adjustment will be done.

Planned subgroup analysis

No subgroup analysis will be done.

Section 5: Outcome Variables

Primary Outcomes

The main outcome of this study is the evaluation of the equivalency of the efficacy of Lunaphil Ultra (Hyaluronic acid, produced by Espad Pharmed Co.) compared to Juvéderm® Ultra 4 (Hyaluronic acid, produced by Allergan Co.), which is measured by evaluate the mean level of improvement from baseline in NLF severity score by WSRS at week 24.

Secondary Outcomes

Evaluating the effectiveness of Lunaphil Ultra (Hyaluronic acid, produced by Espad Pharmed Co.) compared to Juvéderm® Ultra 4 (Hyaluronic acid, produced by Allergan Co.) in the following criteria:

- The number of participants with improved score in Physician Global Aesthetic Improvement Scale (PGAIS) at week 24 compared to baseline which was assessed by two evaluators
- The proportion of NLFs that sustained a clinically meaningful reduction in severity score (≥ 1 -point reduction from baseline) at week 24
- The injected volume to obtain optimal aesthetic result (initial treatment + touch-up)
- The number of NLFs receiving touch-up treatment

Safety outcome

The incidence, severity and causal relationship of adverse events will be reported. The intensity of AEs will be graded according to the CTCAE v5.0, and terminology for AEs will be chosen according to the MedDRA system organ class and preferred term (MedDRA Desktop Browser 4.0 Beta). Seriousness will be also recorded for all AEs.

Section 6: Descriptive statistics

[figure not shown]
Participant flow

The flow of participants throughout the study is planned to be summarized. A participant flow diagram will illustrate the number of subjects at each stage of the study, including:

- Number of subjects randomized to each treatment group
- Number of subjects who received at least one dose of study treatment
- Number of subjects who completed the study and those who discontinued (with reasons)
- Number of subjects included in each analysis set (PP, ITT, Safety)

Tabulations of participant disposition will also be provided, including counts and percentages by treatment arm. The reasons for exclusion from each analysis set will be documented in the subject listings and summarized in the Clinical Study Report (CSR).

All flow and disposition data will be based on the data recorded in the clinical database up to the date of database lock.

Baseline characteristics

Baseline characteristics	Categories
Age	-
Sex	Male/Female
History of filler injection in NLF	Yes/No
WSRS	1 to 5

Descriptive statistics for baseline characteristics will be presented as mean and standard deviation for continuous variables, and as frequency and percentage for categorical variables.

Section 7: Statistical Analysis

This section describes the planned statistical analyses for efficacy and safety outcomes. Results will be summarized using appropriate descriptive statistics and analyzed using suitable statistical models depending on the data type. Treatment effects will be presented with 95% confidence intervals and two-sided p-values, using a significance level of 0.05.

Primary Endpoint Analysis

For the statistical analysis of the primary outcome (equivalence assessment of the mean level of improvement from baseline in NLFs severity score), both categories of Per-Protocol and Intention-to-Treat statistical population will be examined. Although the main approach is the results of the statistical analysis of the Per-Protocol population, eventually a sensitivity analysis will be performed between the results of the said analysis and the results of the statistical analysis of the Intention-to-Treat population.

Paired t-test or a signed-rank test will be used to compare the mean level of improvement from baseline in NLFs severity score based on assessments by evaluating investigators between Lunaphil Ultra (Hyaluronic acid, produced by Espad Pharmed Co.) compared to Juvéderm® Ultra 4 (Hyaluronic acid, produced by Allergan Co.). The 95% confidence interval (CI) for the mean difference between the two treatments will be calculated. Equivalence will be concluded if the entire 95% CI falls within the pre-specified equivalence margin of ± 0.17 .

Secondary Endpoints Analysis

- The number of patients with improvement score for the PGAIS will be analyzed using a McNemar test.
- The proportion of NLFs maintaining a clinically significant improvement will be analyzed using a McNemar test.
- Injection volume to obtain optimal result will be analyzed with a paired t-test or a signed-rank test.

The number of NLFs receiving touch-up treatment will be analyzed using a McNemar test.

Safety Analysis

All adverse events (AEs) data will be descriptively analyzed. Also, AEs in two groups are compared

using Pearson chi-square test.

The incidence and percentage of treatment-emergent adverse events will be reported, categorized by system organ class (SOC) and preferred term (PT). Adverse events' severity, seriousness, and causality assessment will be reported.

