A phase IV, randomized, double-masked, active controlled, within-subject equivalency clinical trial to compare effectiveness and safety of Lunaphil Ultra (Hyaluronic acid, produced by Espad Pharmed Co.) versus Juvéderm® Ultra 4 (Hyaluronic acid, produced by Allergan Co.) for the management of moderate or severe nasolabial folds (NLFs)

Ethics Approval Number

IR.TUMS.MEDICINE.REC.1400.1011

SAP Version (SAP version number with dates)

Version: 1.0, Date: 2021 August 14

Section 2: Introduction

Introduction

This Statistical Analysis Plan (SAP) provides a detailed and comprehensive description of the planned statistical analyses for the Phase IV randomized, double-blind, parallel-group, active-controlled clinical trial designed to assess the therapeutic equivalence in efficacy and safety of Lunaphil Ultra (Hyaluronic acid, produced by Espad Pharmed Co.) versus Juvéderm® Ultra 4 (Hyaluronic acid, produced by Allergan Co.) in managing moderate or severe NLFs.

The objective of this SAP is to outline the statistical methodologies and analysis principles that will be applied to evaluate the primary and secondary endpoints of the study, as well as the handling of missing data, analysis sets, and subgroup analyses. This SAP is intended to ensure transparency and reproducibility of the planned analyses, and it has been finalized prior to database lock and unblinding of the study data.

Rationale and Background

Skin aging is a complex and multifactorial process resulting in various functional and aesthetic changes in the skin (1). It is an inevitable process that can be described clinically as features of wrinkles, sun

spots, uneven skin color, and sagging skin (2). Additional clinical findings include tear trough, a drop of the angle of the mouth, loss of definition in the mandibular border, platysmal bands, evident veins, and NLFs as one of the typical clinical manifestations of facial aging (3).

The perception of health and age is a critical aspect in the common judgment of attractiveness and people are judged to be less attractive as they age (4). Attractiveness influences both self-perception and social behavior and is related to traits such as self-confidence and social acceptance. Therefore, aesthetic interventions can improve psychological well-being and quality of life (5).

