In an equivalence test of means using two one-sided tests on data from a paired design, a sample size of 97 achieved 80% power at a 2.5% significance level. When the true difference between the means was 0.000, the standard deviation of the paired differences was 0.510, and the equivalence limits were -0.170 and 0.170. Considering a drop-out rate of 10%, total sample size required is 108.

Study Population Criteria

Inclusion Criteria

1. Subjects \geq 30 years of age

2. Visible bilateral NLFs that are approximately symmetrical and have an equal severity ranging from moderate to severe (assessed at the deepest part)
3. Able to follow study instructions and likely to complete all required visits
4. Signed informed consent

Exclusion Criteria

1. History of bleeding disorders or participants receiving or recently exposed (≤ 3 weeks) to continuous treatment with thrombolytics, anticoagulants, platelet inhibitors, or NSAIDs
2. Acute herpetic eruption
3. Known susceptibility to keloid formation, hypertrophic scarring or clinically significant skin pigmentation disorders
4. Known sensitivity to local anesthetics of the amide type (such as lidocaine), history of hypersensitivity to gram-positive bacterial proteins, history of multiple severe allergies, history of anaphylactic shock
5. Known hypersensitivity to any component of the study products or excipients (like hyaluronic acid)
6. History of receiving immune therapy or a history of autoimmune disease
7. History of active chronic debilitating systemic disease
8. History of connective tissue disease, history of malignancy (except for non-melanoma skin cancer) within the last 5 years
9. Clinically significant active dermatologic disorders within the last 6 months
10. Use of oral retinoids, OTC or prescription antiwrinkle treatments, microdermabrasion, or chemical peels in the NLF area within the last 4 weeks or intention to use them during the study
11. Any prior cosmetic procedure or tissue augmentation at the NLF injection site within 1 year before study entry (or intent to undergo such a procedure during the study)
12. Pregnancy or breastfeeding

Withdrawal Criteria

1. Withdrawal of consent by the participant
2. Noncompliance, including refusal of study medical requirements, refusal of procedures as stated in the study protocol, or use of prohibited medications
3. The occurrence of an undesirable event that causes the investigator to consider the participant's exclusion from the study

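### The SAP introduction claims an equivalence aim for safety that has no margin, no sizing and no decision rule, and the only named adverse-event test cannot support it

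*SAP*

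**What the plan says.** The SAP introduction (Section 2) says the trial is "designed to assess the therapeutic equivalence in efficacy and safety of Lunaphil Ultra" against the comparator. Elsewhere, equivalence belongs to efficacy:

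- SAP Section 5, Primary Outcomes: "The main outcome of this study is the evaluation of the equivalency of the efficacy of Lunaphil Ultra".
- SAP Section 3, Sample size (and protocol 8.6): "the standard deviation of the paired differences was 0.510, and the equivalence limits were -0.170 and 0.170". These are WSRS quantities.
- SAP Section 7, Primary Endpoint Analysis: "Equivalence will be concluded if the entire 95% CI falls within the pre-specified equivalence margin of ± 0.17".

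Safety is the fifth secondary objective (SAP Section 2) and carries no equivalence wording there. The safety outcome in Section 5 reads "The incidence, severity and causal relationship of adverse events will be reported". The Safety Analysis in Section 7 begins "All adverse events (AEs) data will be descriptively analyzed" and then adds "Also, AEs in two groups are compared", naming the Pearson chi-square test. The SAP synopsis and protocol 8.7.2 plan summary statistics for safety and name no test. Section 7 opens with a general statement, covering efficacy and safety outcomes, that treatment effects will be shown with 95% CIs and two-sided p-values at 0.05.

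Neither document gives a safety margin, an expected adverse-event rate, or a rule for interpreting the adverse-event comparison.

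**The concern.** An equivalence claim needs a margin fixed in advance, an interval judged against it, and enough participants for that interval to be narrow. For safety the plan has none of these. It has an introductory aim that includes safety equivalence and, later, a test of no difference. Failing to reject no difference is not evidence of equivalence, whichever test is used.

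The planned test has a second weakness. Each participant receives both products, one per fold, so adverse events on the two sides are paired. Pearson chi-square treats the sides as independent groups. With positive within-person correlation and no true difference it rejects too rarely, so non-significance tells the reader even less.

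At stake is the safety conclusion. A p-value above 0.05 could be taken to fulfil the introduction's aim while the data remain compatible with a relevant excess on one product.

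**Working it through.** **1. What the sample size covers.** Inputs from SAP Section 3: SD of paired differences 0.510, limits ±0.170, true difference 0, 2.5% per one-sided test, 80% power.

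- Normal approximation: n = [SD × (z0.975 + z0.90) / margin]² = [0.510 × (1.960 + 1.282) / 0.170]² = 94.6, so 95.
- With the t distribution, power is 0.797 at n = 96 and 0.803 at n = 97. The stated 97 reproduces.
- Drop-out: 97 / 0.90 = 107.8, so 108. This also reproduces.

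No adverse-event quantity enters this calculation.

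**2. What a non-significant adverse-event test would mean.** The rates p1 and p2 and the within-person correlation φ below are assumptions. With 108 pairs:

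- P(event on both sides) = p1·p2 + φ√[p1(1−p1)p2(1−p2)].
- For 10% v 5% and φ = 0: 0.005 on both sides; discordant cells 0.095 and 0.045.
- For φ = 0.3: 0.0246 on both sides; discordant cells 0.0754 and 0.0254.

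Exact McNemar power was summed over the number of discordant pairs and their split. Pearson chi-square power was simulated from the same paired cells, with the two sides analysed as independent groups, as the SAP plans.

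| Assumed rates | Pearson chi-square, φ = 0 / 0.3 | Exact McNemar, φ = 0 / 0.3 |
|---|---|---|
| 5% v 10% | 29% / 26% | 21% / 27% |
| 10% v 15% | 20% / 16% | 14% / 19% |
| 20% v 40% | not tabulated | 87% / 96% |

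With 97 evaluable pairs, chi-square power for 5% v 10% is 26% / 22%. So a doubling from 5% to 10% would be missed in roughly three of four trials, while a doubling from 20% to 40% would usually be found.

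**3. Effect of ignoring the pairing.** With no true difference, a 20% rate and 108 pairs, the chi-square test at nominal 5% rejects about 2% of the time at φ = 0.3 and about 0.3% or less at φ = 0.6.

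**4. What a paired interval would show.** With equal rates p, the 95% half-width is 1.96 × √[2p(1−p)(1−φ)/108]. For φ = 0 / 0.3 this gives ±5.8 / ±4.9 points at p = 5%, and ±10.7 / ±8.9 points at p = 20%. Zero events in 108 still allows a true rate up to 1 − 0.05^(1/108) = 2.7% (one-sided 95%).

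**5. What a real safety-equivalence aim would need.** Assume a margin of ±10 points, zero true difference, 80% power and 2.5% per side: n = discordance × (1.960 + 1.282)² / 0.10². With 10%, 30% and 50% discordant pairs this gives 106, 316 and 526 pairs. Unless discordance is low, 97 or 108 pairs would not be enough.

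**The case against.** The strongest reply is that this is one loose phrase in an introduction. The same sentence calls a within-subject trial parallel-group, which suggests template wording. The operative sections already confine equivalence to efficacy, the safety analysis is descriptive first, and the chi-square comparison is an addition. Section 7 also promises 95% CIs for treatment effects. Low power for adverse events is usual in a trial sized on an efficacy endpoint.

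Most of this stands. It shows that the introduction is out of line with the rest of the SAP, and it limits how far the criticism goes. It does not remove the mismatch: the aim is written down, no text disclaims it, and the general CI sentence neither names a paired difference in incidence nor says how it will be interpreted.

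Three stronger readings are tempting, and the documents support none of them:

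- A reader might infer that a non-significant result will be reported as equal safety. No rule says so; the only rule for concluding equivalence names the WSRS difference. That it could be read that way is as far as the text goes.
- A reader might infer that p > 0.05 is the most likely result. That depends wholly on event rates, which the documents do not give; the 20% v 40% case shows the opposite.
- A reader might infer that safety is only tested for a difference. Descriptive summaries of incidence, severity, seriousness and causality are also planned.

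**Conclusion.** The point holds as a mismatch between the SAP's stated aim and its analysis. The introduction claims an equivalence assessment of safety that the design does not contain, and the one named adverse-event test can neither establish equivalence nor respect the paired design. The primary WSRS analysis, its margin and its error rate are untouched.

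The power figures are illustrative. They rest on assumed rates, correlations of 0 to 0.3 and all 108 participants being evaluable. They show that modest differences at low event rates would often go undetected, not that every relevant difference would. The logical point, that a non-significant difference test is not evidence of equivalence, needs none of these assumptions. The correction is worth making because it changes what the trial may conclude about safety.

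**What to change.** - **SAP Section 2, Introduction:** limit the equivalence aim to improvement in WSRS at week 24 and say that safety is compared descriptively.
- **SAP Section 7, Safety Analysis:** state that no equivalence conclusion will be drawn for safety. Replace the chi-square comparison, as the basis for comparing the products, with the within-participant difference in adverse-event incidence and its paired 95% CI. Label any adverse-event p-value, preferably from a paired test, as descriptive.

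This is a change of SAP wording and one line of analysis; it needs no extra participants or data. The downside is that the sponsor gives up an equivalent-in-safety claim. To keep that claim, the sponsor would need a justified safety margin, an interval rule and a power check, which on the illustration above could require several hundred pairs.

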	
platelet inhibitors, or NSAIDs
 
• Acute herpetic eruption• Known susceptibility to keloid formation, hypertrophic scarring or clinically significant skin pigmentation disorders• Known sensitivity to local anesthetics of the amide type (such as lidocaine), history of hypersensitivity to gram-positive bacterial proteins, history of multiple severe allergies, history of anaphylactic shock• Known hypersensitivity to any component of the study drugs or excipients (like hyaluronic acid)• History of receiving immune therapy or a history of autoimmune disease• History of active chronic debilitating systemic disease• History of connective tissue disease, history of malignancy (excl. non-melanoma skin cancer) within past 5 years• Clinically significant active dermatologic disorders within 6 months• Use in the 4 weeks before study randomization (or intent to use during the study) of oral retinoids, OTC or prescription antiwrinkle treatments, microdermabrasion, or chemical peels in the NLF area• Any prior cosmetic procedure or tissue augmentation at the NLF injection site in 1 year before study entry (or intent to undergo such a procedure during the study)• Pregnancy or breastfeeding
Randomization	The subjects will be randomized into two possible treatment groups. The first treatment group will receive Lunaphil Ultra on the right side and Juvéderm® Ultra 4 on the left side of their face. The second treatment group will receive Juvéderm® Ultra 4 on the right side and Lunaphil Ultra on the left side of their face. The randomization plan of the subjects will be carried out centrally using an R-CRAN software version 4.0.3. Blocks (with the size of 2) will be made using permuted block randomization for a total of 108 subjects (1:1 allocation ratio).
Blinding	To prevent the influence of any bias caused by knowing the intervention face-side, the study will be double-blinded. Hence, patients and those who assess the study outcomes will remain unaware of allocation to test- or reference-Hyaluronic acid.
Intervention	Subjects will be treated with Juvéderm® Ultra 4 in one NLF and Lunaphil Ultra in the opposite NLF.

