3. The injected volume to obtain optimal aesthetic result (initial treatment + touch-up)
4. The number of NLFs receiving touch-up treatment
5. The incidence, severity and causal relationship of adverse events

Section 3: Research Methods

Study Design

This is a randomized, double-masked, active controlled, within-subject, and equivalency study to compare the effectiveness and safety of Lunaphil Ultra (Hyaluronic acid, produced by Espad Pharmed Co.) versus Juvéderm® Ultra 4 (Hyaluronic acid, produced by Allergan Co.) for the management of moderate or severe NLFs.

Intervention

Subjects will be treated with Juvéderm® Ultra 4 in one NLF and Lunaphil Ultra in the opposite NLF. Two treatments will be allowed over a 2-week period (initial treatment plus one touch-up) to achieve optimal correction of the NLFs. The level of correction will be assessed by the evaluating investigator at week 2 after the initial treatment and, if less than optimal, the treating investigator will be directed to retreat the undercorrected NLF(s).

Randomization

The subjects will be randomized into two possible treatment groups. The first treatment group will receive Lunaphil Ultra on the right side and Juvéderm® Ultra 4 on the left side of their face. The second treatment group will receive Juvéderm® Ultra 4 on the right side and Lunaphil Ultra on the left side of their face. The randomization plan of the subjects will be carried out centrally using an R-CRAN software version 4.0.3. Blocks (with the size of 2) will be made using permuted block randomization for a total of 108 subjects (1:1 allocation ratio).

Blinding

To prevent any bias arising from awareness of face-side allocation, this study will be performed in a double-blind manner. For each participant, one side of the face will receive the investigational hyaluronic acid product and the other side will receive the reference Hyaluronic acid product, according to the pre-specified randomization plan. Both the participants and all investigators responsible for administering injections and assessing outcomes will remain blinded to the allocation throughout the study.

Sample size

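### One fixed block size of 2 for side assignment means that one unmasked participant can reveal another; randomly varying, undisclosed sizes would limit this at almost no cost

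*SAP*

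**What the plan says.** What is randomised is which side of the face receives which product; every participant receives both. SAP Section 3 (Randomization) states: "Blocks (with the size of 2) will be made using permuted block randomization for a total of 108 subjects", at 1:1, from a list produced centrally in R. The Randomization row of the SAP synopsis says the same. No stratification and no variation in block size are described, and nothing is said about who may know the size. The protocol text available for review gives neither a block size nor a randomisation method.

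On masking, SAP Section 3 (Blinding) covers participants and also says that "all investigators responsible for administering injections and assessing outcomes will remain blinded to the allocation throughout the study".

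The outcomes that depend on this masking are ratings. The primary analysis uses the "NLFs severity score based on assessments by evaluating investigators" (SAP Section 7). PGAIS is a measure "which was assessed by two evaluators" (SAP Section 5). Touch-up depends on a judgement as well: "The level of correction will be assessed by the evaluating investigator at week 2 after the initial treatment" (SAP Section 3, Intervention).

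**The concern.** A 1:1 block of two holds exactly one participant of each side order. Anyone who knows the size and the list order, and learns one participant's allocation, therefore knows the block-mate's allocation too. A single lapse in masking can spread to a second participant with no further lapse.

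Both folds are on one face and are scored by the same evaluator. An evaluator who knew the side would know which product is in which fold. That could tilt the WSRS and PGAIS ratings. It could also tilt the week-2 judgement of under-correction, which feeds two further secondary outcomes: injected volume and number of folds touched up.

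**Working it through.** **1. The plan's own figure.** Inputs (SAP Section 3, Sample size): SD of paired differences 0.510, limits ±0.170, true difference 0, two one-sided tests at 2.5%, 80% power, 10% drop-out. Exact paired TOST power is 79.7% at n = 96 and 80.3% at n = 97, so 97 reproduces. 97/(1 − 0.10) = 107.8, rounded up to 108, also reproduces. Block size does not enter this calculation.

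**2. What one leak says about a block-mate.** In a 1:1 block of size 2m, the chance that a given block-mate has the opposite side order is m/(2m − 1):
- size 2: 1/1 = 100%
- size 4: 2/3 = 67%
- size 6: 3/5 = 60%

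**3. Ceiling: all earlier allocations known.** In blocks of 2 the second member is always certain, so 54 of 108 (50%) are certain. The best guess is right 0.5 × 1 + 0.5 × 0.5 = 75% of the time. For a shuffled list of 12 fours and 10 sixes (48 + 60 = 108), simulation with a guesser who knows the make-up but not the order gives about 7 of 108 certain and about 69% correct. The varied list removes most certain deductions but improves overall guessing only modestly.

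**4. Scattered leaks, with size and list order known.** The number of leaks L is an assumption. With blocks of 2, each leaked participant's mate is not itself leaked with probability (108 − L)/107, so the expected number of further participants revealed is L(108 − L)/107. In the 4/6 list a further participant becomes certain only when all of one side order in a block has leaked (two of a four, three of a six). That column is from 20,000 simulations with every block boundary known.

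| Leaks L | Blocks of 2 | Shuffled 4/6 list |
|---|---|---|
| 1 | 1 × 107/107 = 1.0 | 0 |
| 5 | 5 × 103/107 = 4.8 | 0.1 |
| 10 | 10 × 98/107 = 9.2 | 0.4 |

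**5. Effect on the primary result: illustration only.** The documents give no basis for a rating bias. Assume a same-direction bias b in every participant whose side is known. The leaked participants carry it as well as their block-mates, so the right baseline is leaks alone, not the unbiased 80.3%. The mean shift is bL/108 for leaks alone and b(L + extra)/108 with block-mates. Exact TOST power at n = 97:

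| L | b | Shift, leaks alone | Power | Shift, with block-mates | Power |
|---|---|---|---|---|---|
| 5 | 0.25 | 0.0116 | 79.2% | 0.0227 | 76.2% |
| 10 | 0.10 | 0.0093 | 79.6% | 0.0177 | 77.8% |
| 10 | 0.25 | 0.0231 | 76.0% | 0.0443 | 65.5% |

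**6. What blocks of 2 buy.** Their benefit is tight left/right balance: the running difference never exceeds 1, against up to 3 for the 4/6 list. Both lists end 54:54. The primary analysis is per-protocol (SAP Section 4), and the plan allows for losing 108 − 97 = 11. If the 11 are lost at random from 54:54, the left/right difference has variance 4 × 11 × ¼ × 97/107 = 9.97, so SD 3.2. The hypergeometric chance of a difference of 3 or more is 53%. Exact balance is therefore unlikely to survive into the primary analysis in any case.

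**The case against.** Blocks of 2 at 1:1 are a legitimate scheme, and nothing in the documents contradicts them. Harm needs a chain of events: someone knows the size, knows the list order, a participant is unmasked, the knowledge reaches an evaluator, and that evaluator scores differently because of it. The documents show none of these. The list is central, and Section 3 masks participants, injectors and assessors throughout. The usual reason for hiding block size is also weak here: because everyone receives both products, foreknowledge cannot steer anyone towards or away from a product. If unmasking were systematic, for example through recognising a product, sides would be known directly and block size would add nothing. All of this stands, and it sets the priority of the point.

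Three stronger readings are tempting and are not supported:
- **That sites know the block size because the SAP prints it twice.** The documents do not say that evaluators receive the SAP, and the protocol text available does not give the size. Silence about withholding is not disclosure.
- **That the injector is unmasked because the synopsis says only that** "patients and those who assess the study outcomes will remain unaware of allocation to test- or reference-Hyaluronic acid". This is a shorter description than Section 3, not a contradiction of it, and it lends no weight here.
- **That the primary result is biased or loses a stated amount of power.** Both the number of leaks and the bias in step 5 are assumed.

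**Conclusion.** The point holds as a low-priority design improvement, not as an error in the plan. It is certain that, given knowledge of size and order, a fixed size of 2 turns one unmasked participant into two, and that a varied list nearly removes this (9.2 against 0.4 further participants at 10 leaks). It is equally certain that block size reveals nothing if masking holds.

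The leak counts assume scattered, partial unmasking. The consequence for the equivalence conclusion cannot be derived from the documents. On the assumed biases in the working, the added loss of power runs from about 2 percentage points (10 leaks, 0.1 points) to about 10 (10 leaks, 0.25 points). Sample size and planned power do not change.

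**What to change.** **If the allocation list is not yet in use:** generate it centrally with randomly varying block sizes, for example 12 blocks of 4 and 10 blocks of 6 in random order, which fills 108 and ends 54:54. In the SAP, describe it only as permuted blocks of randomly varying size, and keep the sizes in a restricted document that site staff cannot see. The cost is a few lines of R, one line of SAP text, and a running left/right difference of up to 3 instead of 1.

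**If randomisation has begun:** leave the list unchanged and report the fixed block size of 2 as a limitation. This may well be the case that applies. Enrolment status is not stated, and the SAP is dated August 2021 but its reference list gives access dates in August 2024.
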